5. ANALYSIS DATA SETS

Only subjects who sign informed consent and are screened will be included in the analysis sets below.

The following analysis sets will be evaluated and used for presentation of the data:

- The Full Analysis Set (FAS) will include all subjects who are randomized. Subjects will be classified according to the randomized treatment arm. (Note: this data set is referred to as the Intent-to-Treat Analysis Set in the protocol.)
- The Safety Analysis Set will include all subjects who receive at least 1 dose of the study treatment. Subjects will be classified according to the treatment received, where treatment received is defined as:
 - The randomized treatment if it is received at least once, or
 - The first treatment received if the randomized treatment is never received
- The Per-Protocol Set (PPS) is a subset of the FAS. Subjects who meet any of the following criteria will be excluded from the PPS:
 - Do not receive at least 1 dose of the randomized treatment
 - Eligible for intensive chemotherapy (IC) (ie, do not meet Inclusion Criterion 1)
 - Do not have an IDH1 mutation as determined by central laboratory testing (ie, do not meet Inclusion Criterion 3)
 - Have an ECOG PS score >2 (ie, do not meet Inclusion Criterion 4)
 - Have received any prior treatment for AML with the exception of noncolytic treatments to stabilize disease such as hydroxyurea or leukapheresis (ie, do not meet Exclusion Criterion 2)
 - Have received any prior hypomethylating agent (ie, do not meet Exclusion Criterion 3)
 - Have received any prior IDH1 inhibitor (ie, do not meet Exclusion Criterion 5)
- The Biomarker Analysis Set (BAS) is a subset of the FAS and will include all subjects who have at least 1 on-treatment biomarker sample providing valid IDH1m variant allele frequency (VAF) data.

Table 2 summarizes the use of the analysis sets.

Table 2: Analysis Sets for Each Endpoint

Endpoints	Full Analysis Set (FAS)	Per-Protocol Set (PPS)	Safety Analysis Set	Biomarker Analysis Set (BAS)
Demographic and other baseline characteristics	✓		✓	
Disposition	✓			
Major protocol deviations	✓			
Subsequent therapies	✓			
Exposure and concomitant therapies			✓	
Efficacy	✓	✓ (primary and key secondary only*)		
Safety			✓	
Biomarkers				✓

* Key secondary endpoints are CR, OS, CR+CRh and objective response (OR).

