12.2. Analysis Sets

The following analysis sets will be evaluated and used for presentation of the data:

- Intent-to-Treat (ITT) Analysis Set: All subjects who are randomized. Subjects will be classified according to the randomized treatment arm. The ITT Analysis Set will be the default analysis set for all analyses, unless otherwise specified.
- Safety Analysis Set (SAS): All subjects who received at least 1 dose of the study treatment. Subjects will be classified according to the treatment received. The SAS will be the primary analysis set for all safety analyses, unless otherwise specified.
- Per-Protocol Analysis Set (PPAS): All subjects in the ITT who have no major protocol deviations. Additional efficacy analyses may be performed using the PPAS. Rules for major protocol deviations resulting in exclusion from the PPAS will be specified in the SAP.
- Pharmacokinetic Analysis Set (PAS): All subjects who have at least 1 post-dose blood sample providing evaluable PK data for AG-120.

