12.5.2. Analyses of the Secondary Endpoints

The key secondary efficacy endpoints are CR rate, OS, CR + CRh rate, and ORR. Additional secondary efficacy endpoints include CR + CRi (including CRp) rate, DOCR, DOCRh, DOR, DOCRi, TTCR, TTCRh, TTR, TTCRi, transfusion requirements (platelet and RBC), rates of infection, days hospitalized, other efficacy and safety measures that are potentially indicative of clinical benefit, change from baseline in QoL assessments, and the rates of CR with IDH1 MC.

Sensitivity analyses and subgroup analyses for the secondary efficacy endpoints will be specified in the SAP.

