7.7. Efficacy Analyses

The following analyses will be based on the FAS using the IRT randomization stratification factors, unless otherwise specified.

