7.9. Biomarker Analyses

7.9.1. Methods

Genomic DNA from baseline and on-treatment bone marrow mononuclear cells (BMMCs) and/or peripheral blood mononuclear cells (PBMCs) will be used for molecular studies. mIDH1 VAF will be quantified through BEAMing digital PCR (dPCR) technology (OncoBEAM™; Sysmex Inostics, Baltimore, MD, USA) for assessment of R132 (C/G/L/S/H) alleles. A valid mIDH1 VAF result is defined as a VAF value other than “not evaluable”. IDH1 MC is defined as mIDH1 VAF reduction to below the lower limit of detection (0.02%-0.04%) for at least one on-treatment time point.

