7.9.2. Statistical Analyses

Complete remission with IDH1 MC is defined as a response of CR where there is no evidence of the IDH1 mutation by molecular techniques to below the lower limit of detection (0.02%-0.04%) for ≥ 1 on-treatment time point. A CMH test stratified by the randomization stratification factors will be used to compare the rate of CR with IDH1 MC between the 2 treatment arms and the nominal 1-sided p-value will be presented. The odds ratio and its associated 95% CI will be presented.

IDH1 MC by sample type (BMMCs and PBMCs) and treatment arm will be summarized in a table by best objective response. The difference in percent of subjects who achieved IDH1 MC in each sample type and treatment arm will be compared between subjects achieving CR to subjects not achieving CR as best objective response using a Fisher’s exact test.

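### As the SAP is laid out, the between-arm test of CR with IDH1 mutation clearance runs in the Biomarker Analysis Set, while the protocol points to all randomized subjects

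*SAP*

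**What the plan says.** **SAP.** Section 5 defines the Biomarker Analysis Set (BAS): "The Biomarker Analysis Set (BAS) is a subset of the FAS and will include all subjects who have at least 1 on-treatment biomarker sample" that yields valid IDH1 variant allele frequency (VAF) data. Section 7.9.1 explains validity: "A valid mIDH1 VAF result is defined as a VAF value other than" not evaluable. In Table 2 the Biomarkers row is ticked under the BAS alone, while the Efficacy row is ticked under the FAS. Section 7.9.2 specifies a stratified CMH test to "compare the rate of CR with IDH1 MC between the 2 treatment arms and the nominal 1-sided p-value will be presented", plus an odds ratio with its 95% CI, and names no analysis set. The FAS rule is "The following analyses will be based on the FAS using the IRT randomization stratification factors, unless otherwise specified", but it opens section 7.7, and this test is in 7.9.

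**Protocol.** Section 12.5.2 lists the additional secondary efficacy endpoints, ending with "change from baseline in QoL assessments, and the rates of CR with IDH1 MC". The test itself is described in 12.5.2.2.6, inside Efficacy Analyses. Section 12.2 says "The ITT Analysis Set will be the default analysis set for all analyses, unless otherwise specified", and its list of analysis sets contains no biomarker set. Section 12.5 leaves this endpoint outside the fixed testing sequence, with no alpha control.

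**The concern.** A comparison of randomized arms should keep everyone randomized in the denominator. BAS membership is settled after randomization: a subject must be dosed and must give a usable sample during the on-treatment period. Those who leave are subjects never dosed, subjects who die or stop early with no qualifying sample, and subjects whose results are all not evaluable. None of them can be counted as CR with clearance, because clearance requires a VAF below detection at one or more on-treatment time points.

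The set therefore removes subjects from the denominator and never from the numerator. CR would be reported on all randomized subjects, and its subset, CR with clearance, on a smaller denominator that depends on outcome. Both would carry odds ratios that look comparable. A treatment-effect p-value would rest on a non-randomized subset.

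**Working it through.** **1. The plan's own figures.** The documents give no expected rate, power or exclusion share for this endpoint, so there is no figure of its own to reproduce. The neighbouring figures do reproduce. For CR at 40% vs 20%, 100 per arm, 1-sided 2.5%, a two-proportion calculation gives 87.6% power (88.5% unpooled, 84.0% with continuity correction), against 86% stated. For OS, 145 deaths and HR 0.71 give 54.1%, against 54% stated. The response-rate powers use all 200 randomized subjects.

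**2. Loss that can be anchored in the documents.** Inputs: median OS 10.4 months (control) and 14.6 months (AG-120), exponential (SAP 6.2.1); first scheduled post-baseline marrow and blood at Week 9 Day 1 ± 7 days (Protocol Table 6, footnotes 12 and 13); 1 month = 30.4375 days (SAP 6.4.2).

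Share dead by time t = 1 − exp(−ln 2 × t / median).

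- Day 56 (1.84 months): control 11.5%, AG-120 8.4%.
- Window limits: day 49 gives 10.2% and 7.4%; day 63 gives 12.9% and 9.4%.

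**3. Effect on the odds ratio.** Let p be the FAS rate and m the share with no valid sample. All excluded subjects are non-events, so the BAS rate is p/(1 − m) and the BAS odds are p/(1 − m − p). The rates below are assumed, because the documents give none: control 5%, AG-120 20%, FAS odds ratio (0.20/0.80)/(0.05/0.95) = 4.75.

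| Loss, control / AG-120 | Basis | BAS odds ratio |
|---|---|---|
| 11.5% / 8.4% | OS medians, day 56 | (0.20/0.716)/(0.05/0.835) ≈ 4.66 |
| 20% / 10% | assumed | (0.20/0.70)/(0.05/0.75) = 4.3 |
| 30% / 15% | assumed | (0.20/0.65)/(0.05/0.65) = 4.0 |
| 15% / 25% | assumed | (0.20/0.55)/(0.05/0.80) = 5.8 |

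Across the visit window the first row runs from 4.67 (day 49) to 4.65 (day 63). Rounding the losses to 11 and 8 per 100 also gives 4.67.

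**4. Effect on the p-value.** Assume 20 (AG-120) and 10 (control) CR-with-clearance subjects per 100 randomized, with an unstratified test. The FAS gives odds ratio 2.25, 1-sided p = 0.024. Excluding 8 AG-120 and 11 control subjects gives 2.19, p = 0.029. Excluding 15 and 30 gives 1.85, p = 0.074. Excluding 30 and 15 gives 3.00, p = 0.004. With equal counts of 15 and 15, excluding 15 and 30 gives 0.79, and excluding 30 and 15 gives 1.27.

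**The case against.** **The set is inferred, not stated.** SAP 7.9.2 names none. The BAS reading rests on a one-word row in Table 2 and on where the test is placed; the protocol's efficacy classification and the Efficacy row of Table 2 support the FAS. The protocol default also allows exceptions, and SAP section 2 lets the SAP modify protocol plans, so using another set is not in itself a breach. This stands. But Table 2 ticks no other set for biomarkers, so BAS is the plain reading, and an unresolved choice of denominator needs the same repair.

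**Early stopping does not by itself mean exclusion.** A reader might infer that everyone who stops before Week 9 is dropped. The documents do not support that. The EOT visit falls within 1 week of the last dose, blood sampling is listed at EOT, VAF may come from marrow or blood, and the on-treatment period extends 28 days past the last dose (SAP 6.3.5, 7.9.1; Protocol Table 6). An EOT sample can qualify. On the other side, EOT marrow is not required if one was taken in the prior 8 weeks. Part of the sampling text is redacted, so actual loss cannot be determined.

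**Not every excluded subject is a known failure.** The BAS also drops subjects in CR whose VAF is missing; their clearance status is unknown. Counting them as not cleared is a convention, and it can bias the comparison if sampling among CR subjects differs by arm. This stands as a cost of the fix.

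**The stakes are limited.** The p-value is nominal, and no power calculation depends on this endpoint.

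**Conclusion.** The point holds: as laid out, a between-arm test of a protocol-classified efficacy endpoint runs on a subset defined by post-randomization survival, dosing and sampling. That only non-events are removed follows from the definitions and needs no assumption. The size does rest on assumptions. The one document-anchored component, death before Week 9, moves the illustrative odds ratio from 4.75 to about 4.66. It is not an estimate of total loss, which could be lower (qualifying samples taken before death) or higher (never-dosed, withdrawn or not-evaluable subjects). Larger or more unequal loss moves the ratio more: 4.0 to 5.8 in the assumed patterns.

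A reader might infer that the BAS flatters AG-120. The documents do not support a fixed direction. In the illustration, the greater early mortality that the plan assumes for control pulls the odds ratio slightly against AG-120; inflation in AG-120's favour would need heavier loss in that arm. Nor do the primary or key secondary tests suffer: they use the FAS, and this endpoint is outside the fixed sequence. This should be corrected, but it does not threaten the trial's main conclusions.

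**What to change.** In SAP Table 2 and section 7.9.2, name the FAS for the CMH test and odds ratio of CR with IDH1 clearance, and state that subjects without a valid on-treatment VAF result count as not having CR with clearance. Report by arm the number of CR subjects with missing VAF, so that the effect of this rule is visible. Keep the BAS version of the comparison as supportive, and keep the BAS for descriptions of VAF.

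The cost is SAP wording; no new data are needed. The downside is that CR subjects lacking a valid sample count as failures, so the reported rates will be somewhat lower.

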6. GENERAL STATISTICAL CONSIDERATIONS

6.1. Randomization, Blinding, Unblinding, and Crossover

Subjects will be randomized in a 1:1 ratio to one of the following treatment arms:

- AG-120+azacitidine=AG-120 500 mg QD orally plus azacitidine 75 mg/m²/day SC or IV
- Placebo+azacitidine=AG-120-matched placebo QD orally plus azacitidine 75 mg/m²/day SC or IV

Randomization assignment will be implemented by interactive response technology (IRT) and stratified by:

- AML status (de novo AML; secondary AML)
- Geographic region (United States and Canada; Western Europe, Israel, and Australia; Japan; ROW)

This is a double-blind study therefore the subjects, Investigators, Sponsor, and the clinical research unit staff who work directly with subjects will all be blinded to study treatment assignment.

At the time of the DBL for the final analysis of the primary endpoint, the study will be unblinded. Subjects on treatment at that time may continue receiving study treatment.

After unblinding, and if the benefit-risk profile favors AG-120+azacitidine, subjects randomized to placebo+azacitidine may be offered the choice to receive AG-120.

6.2. Sample Size Determination and Decision Rules

6.2.1. Sample Size Determination

The following statistical hypothesis will be tested to address the primary objective:

$$H_{01}: S_{EFS_T}(t) \leq S_{EFS_C}(t) \text{ vs. } H_{11}: S_{EFS_T}(t) > S_{EFS_C}(t), t \geq 0$$

where $S_{EFS_T}(t)$ is the survival distribution function of EFS in the AG-120+azacitidine arm (referred as treatment arm) and $S_{EFS_C}(t)$ is the survival distribution function of EFS in the placebo+azacitidine arm (referred as control arm).

In addition, the following statistical hypotheses will be tested to address the key secondary objectives:

$$H_{02}: OddsRatio_{(CR)}=1 \text{ vs } H_{12}: OddsRatio_{(CR)}>1$$

where $OddsRatio_{(CR)}$ is the ratio of the odds of CR between the treatment arm and the control arm.

$$H_{03}: S_{OS_T}(t) \leq S_{OS_C}(t) \text{ vs } H_{13}: S_{OS_T}(t) > S_{OS_C}(t), t \geq 0$$

where $S_{OS_T}(t)$ is the survival distribution function of OS in the treatment arm and $S_{OS_C}(t)$ is the survival distribution function of OS in the control arm.

H_{04} : $\text{OddsRatio}_{(\text{CR}+\text{CRh})}=1$ vs H_{14} : $\text{OddsRatio}_{(\text{CR}+\text{CRh})}>1$

where $\text{OddsRatio}_{(\text{CR}+\text{CRh})}$ is the ratio of the odds of CR+CRh between the treatment arm and the control arm.

H_{05} : $\text{OddsRatio}_{(\text{OR})}=1$ vs H_{15} : $\text{OddsRatio}_{(\text{OR})}>1$

where $\text{OddsRatio}_{(\text{OR})}$ is the ratio of the odds of OR between the treatment arm and the control arm.

To control the overall Type 1 error rate at the 1-sided 2.5% level, the fixed sequence testing procedure (Westfall and Krishen, 2001) will be used to adjust for multiple statistical testing of the primary and key secondary efficacy endpoints. These endpoints will be tested in the following order:

- EFS
- CR
- OS
- CR+CRh
- OR

No interim analyses for efficacy are planned.

A total of approximately 200 subjects with previously untreated IDH1m AML will be randomized in this study. The calculations and simulations described below were performed using East Version 6.05 and R Version 3.4.4.

Primary Endpoint - EFS

Based on the definition of EFS, subjects who do not achieve CR by 24 weeks [treatment failure (TF)] will be considered to have had an EFS event on the day of randomization; for subjects who achieve CR by 24 weeks (responders), EFS will be the time from randomization to the earliest of relapse from remission or death from any cause. Whereas it is reasonable to assume that EFS for responders in each treatment arm will follow an exponential distribution, this assumption will be clearly violated for the EFS endpoint which includes both TF and responders components as described below.

Assumptions for the placebo+azacitidine arm are based on results from Study AZA-AML-001 in newly diagnosed AML subjects who are ineligible for IC receiving azacitidine. Data from Study AZA-AML-001 were obtained under a data exchange agreement with Celgene (now Bristol-Myers Squibb), and based on results from a retrospective analysis of these data, the following are assumed in this study:

- CR rate at 24 weeks=20%
- Median EFS=14.6 months, for subjects who achieve CR by 24 weeks

Assumptions for the AG-120+azacitidine arm are based on results from Study AG-221-AML-005 in newly diagnosed AML subjects who are ineligible for IC receiving AG-120 in combination with azacitidine:

[figure not shown]
- CR rate at 24 weeks=40%

- Median EFS=19.2 months, for subjects who achieve CR by 24 weeks; assuming an exponential distribution, this corresponds to a hazard ratio (HR) of 0.76 for the estimated effect of treatment compared to control.

The EFS curves for both the placebo+azacitidine and AG-120+azacitidine arms based on the above assumptions are displayed in [Figure 2](#). Censoring and dropout considerations are not included in the diagram for simplicity. The EFS curve has 2 distinct components with the first component driven by the subjects who have TF and the second component driven by responders.

The treatment effects for the 2 components are clearly distinct and the assumption of proportional hazards will be violated. Therefore, instead of the overall HR, the assumptions for EFS are presented for the 2 components separately. Based on simulation results, the average overall HR over 10,000 simulations for the entire population is 0.641. However, the overall HR for the entire population was not part of the study design assumptions. Additionally, based on the current assumptions, for the overall population, the median EFS will be 1 day for both the placebo+azacitidine and AG-120+azacitidine arms.

Figure 2: Event-Free Survival under Protocol Assumptions

Abbreviations: EFS = event-free survival.

Under these assumptions, a total of 173 EFS events in approximately 200 randomized subjects with previously untreated IDH1m AML are required to provide 80% power at a 1-sided 2.5% level of significance to reject H_{01} using a stratified log-rank test (Table 3).

Table 3: Study Design Parameters for EFS

Design Parameters and Outcomes	
Power	80%
Significance level (1-sided)	2.5%
CR rate by 24 weeks (treatment vs control)	40% vs 20%
HR (treatment vs control) that can be detected for subjects who achieve CR by 24 weeks	0.76
Median EFS for subjects who achieve CR by 24 weeks (treatment vs control)	19.2 vs 14.6 months
Number of subjects randomized (1:1)	200
Target number of EFS events	173 EFS events
Accrual rate	3 subjects/month for the first 10 months, 5 subjects/month thereafter
Accrual time	44 months
Dropout rate	5%
Time to final analysis under H_{11}	52 months after first subject randomized

Abbreviations: CR = complete remission; EFS = event-free survival; HR = hazard ratio.

Overall Survival

Based on available data (Dombret et al, 2015), the median OS in the placebo+azacitidine arm is assumed to be 10.4 months. A target HR of 0.71 for OS (equivalent to a median OS of 10.4 months in the placebo+azacitidine arm vs 14.6 months in the AG-120+azacitidine arm, assuming an exponential distribution) is assumed. Based on 200 randomized subjects and the above assumptions, it is estimated that at the time of the final analysis for EFS, approximately 145 deaths will be observed. With 145 deaths, the study will have 54% power to detect a HR for OS of 0.71 at a 1-sided 2.5% level of significance using a stratified log-rank test.

CR, CR+CRh, and OR

Based on a retrospective analysis of Study AZA-AML-001, the response rates in the placebo+azacitidine arm are assumed to be 20%, 25%, and 32% for CR, CR+CRh, and OR, respectively.

Based on 200 randomized subjects, the power for the analysis of each of these endpoints at a 1-sided 2.5% level of significance to reject the corresponding null hypotheses using a Cochran-Mantel-Haenszel (CMH) test are presented in Table 4.

Table 4: Power for Analyses of CR, CR+CRh, and OR

Endpoints	Number of Subjects	Assumed Response Rate under the Alternative Hypothesis (Treatment vs Control)	Power
CR	200	40% vs 20%	86%
CR+CRh	200	45% vs 25%	84%
OR	200	52% vs 32%	81%

Abbreviations: CR = complete remission; CRh = complete remission with partial hematologic recovery; OR = objective response; vs = versus.

6.2.2. Decision Rules

The final analysis for the primary and key secondary efficacy endpoints will be performed after all subjects have been randomized in the study and followed for a minimum of 24 weeks and the target number of events for EFS has occurred (see [Section 2](#)).

The basis for a claim of efficacy will be the statistical significance of EFS in favor of the AG-120+azacitidine arm when the 1-sided p-value <0.025. To protect the integrity of the study and to preserve the Type 1 error at or below 1-sided $\alpha=0.025$, a hierarchical testing strategy will be used as described in [Section 6.2.1](#) to test each of the key secondary efficacy endpoints and statistical significance will be achieved with 1-sided p-value <0.025 for each endpoint.

6.3. Definitions

6.3.1. Study Drug and Study Treatment

Study drug is defined as AG-120 or matched placebo or azacitidine.

Study treatment is defined as AG-120+azacitidine or matched placebo+azacitidine.

6.3.2. Start and End Dates of Study Drug and Study Treatment

The **start of study drug** (AG-120 or matched placebo or azacitidine) is the earliest date of administration of a non-zero dose of the study drug.

The **end of study drug** (AG-120 or matched placebo or azacitidine) is the latest date of administration of a non-zero dose of the study drug on or before the data cutoff date.

The **start of study treatment** is the earliest of the non-missing start of any study drug.

The **end of study treatment** is the latest of the non-missing end of any study drug.

6.3.3. Study Day

The study day for assessments or events occurring on or after the start of study treatment (eg, AE onset, disease/response assessment) will be calculated as:

$$\text{Study day} = \text{Date of the assessment or event} - \text{start of study treatment} + 1.$$

The study day for assessments or events occurring before the start of study treatment (eg, baseline characteristics, medical history) will be negative and calculated as:

Study day=Date of the assessment or event–start of study treatment.

There is no study day 0. The study day will be displayed in data listings.

